## 7.2 Analysis populations

All patients who signed informed consent / were assigned a randomization number are considered as enrolled/randomized patients, even if they did not receive any trial treatment. The following data sets will be analyzed:

Full Analysis Set (FAS): The primary efficacy analysis will be based on the Intention-To-Treat (ITT) population. All randomized patients who received at least one dose of trial treatment and with at least one available post-baseline assessment of the primary analysis variable will be included in the full analysis set and will be regarded as ITT population. This population is the primary analysis population. Within ITT population analyzes, patients will be assigned to the treatment to which they were randomized.

Per-protocol analysis set (PPS): The per-protocol analysis set will consist of all patients in the full analysis set without major protocol deviations. Patients with major protocol deviations will be excluded from the PPS.

Safety analysis set: The safety analysis set comprises all patients who received at least one dose of trial treatment. In analyzes of the safety population, patients will be assigned to the treatment which they actually received.

The classification of minor and major protocol deviations and the resulting definition of analysis sets will be provided prior to final statistical analysis and prior to unblinding of the study and will be approved by the sponsor. The primary analysis set for the efficacy evaluation is the full analysis set.

A more detailed description of protocol deviations and analysis sets will be included in the statistical analysis plan which will finalized before unblinding treatment allocation and before start of statistical analyzes.

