## 6 TRIAL METHODS

#### 6.1 Assessment of efficacy

Efficacy variables:

- Survival / date of death requiring a death certificate
- ALSFRS-R
- SEIQoL
- sVC

The Efficacy variables listed above will be determined at the study site using standard methods.

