## 7.3.1 Definition and analysis of primary endpoint

The primary endpoint is survival time, i.e. the time until death or the time until last contact to patient. Mortality is exclusively defined as death. Survival time will be calculated as difference from date of last contact and date of randomization. Date of last contact is defined as

- date of death for patients who will die during trial
- date of study termination for patients who are alive if date of study termination > date of last visit, otherwise the date of last visit will be used as date of last contact

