### Replacement of missing values for ITT analysis:

Date of death will be known for all patients who will die during trial. For patients who are alive at end of study/last contact, the following replacement of missing date will be performed. Any date of last contact with unknown day (xx/NA/xxxx) in patients who are alive will be replaced with the date for mid-month (xx/15/xxxx). Dates of last contact with unknown day and month or with unknown day and month and year will not be replaced.

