### Analysis of primary endpoint:

The statistical hypotheses are the following:

 $H_0: \qquad \lambda_2/\lambda_1 {\geq} 1$ 

 $H_1$ :  $\lambda_2/\lambda_1 < 1$ 

where  $\lambda_2/\lambda_1$  is the hazard ratio,  $\lambda_1$  denotes the hazard in the control group,  $\lambda_2$  denotes the hazard in the experimental group. The hazard ratio is assumed to be constant across time. The null hypotheses will be tested using the logrank test. The type one error is set to alpha=0.025 (one-sided). For estimating the treatment effect, the hazard ratio, incl. the one-sided 97.5% confidence interval will be provided.

Only the ITT analysis of the primary endpoint will be regarded as confirmatory. All other analyzes of primary endpoint will be regarded as exploratory.

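### Section 7.2 labels as ITT, and uses for the only confirmatory test, a modified set that leaves out randomised patients without a dose or a post-baseline assessment

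*Protocol*

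**What the plan says.** Protocol Section 7.2 sets two conditions for the primary population beyond randomisation: the patient "received at least one dose of trial treatment and with at least one available post-baseline assessment of the primary analysis variable". Patients who meet both "will be included in the full analysis set and will be regarded as ITT population". Under the analysis of the primary endpoint, Section 7.3.1 adds: "Only the ITT analysis of the primary endpoint will be regarded as confirmatory".

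The opening of Section 7.2 is wider. Patients with a randomisation number "are considered as enrolled/randomized patients, even if they did not receive any trial treatment". Such undosed patients then enter none of the three listed sets: the full analysis set and the safety set both require a dose, and the per-protocol set is drawn from the full analysis set.

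The endpoint runs from randomisation. Section 7.3.1 states: "Survival time will be calculated as difference from date of last contact and date of randomization". For living patients the end date is the study termination date or the last visit, whichever is later. On deaths, the rule for missing values says: "Date of death will be known for all patients who will die during trial". Section 6.1 lists the efficacy variable as "Survival / date of death requiring a death certificate".

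**The concern.** An ITT comparison keeps every randomised patient in the arm assigned, so that the groups compared are those that randomisation made alike. Section 7.2 claims that name for a set built partly on events after randomisation: taking a tablet, and having an assessment on record. For a mortality endpoint counted from randomisation, neither is needed to compute a patient's survival time. The rule can therefore discard a known death or known time alive.

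The second condition is also unclear. A post-baseline assessment makes sense for a scale score. For time to death it could mean any knowledge of vital status after randomisation, including the death itself, or it could mean a completed call or visit. The protocol does not choose. At stake is whether the single confirmatory result can be reported as ITT, and whether early deaths are all counted.

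**Working it through.** **Who is kept, by type of randomised patient**

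| Patient | Survival time available under 7.3.1? | In the 7.2 set? |
|---|---|---|
| No dose, dies | Yes | No |
| No dose, alive with later contact | Yes | No |
| Dosed, dies before the first contact | Yes | Yes if a death counts as an assessment; no if a completed contact is needed |
| Dosed, leaves alive early, termination date recorded | Yes | Not stated |
| Dosed, no later information | Only as censored at randomisation | No |

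The last row does not matter numerically. A patient censored at time 0 is in no risk set when a death occurs and adds nothing to the log-rank statistic.

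**The plan's own figures** (Section 7.1: 18-month survival 70% and 85%, one-sided alpha 0.025, power 0.80, 6 months recruitment, 18 months follow-up)

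- Implied hazard ratio: ln 0.85 / ln 0.70 = 0.456.
- The Lakatos log-rank method with exponential hazards gives 212 patients (power 0.802), matching the protocol.
- 212 / 0.85 = 249.4, so 250; 250 / 0.90 = 277.8, so 278. Both match.

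**Expected early deaths**, with constant hazards and 125 patients per arm

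- Control: 0.3567 / 18 = 0.0198 per month. Experimental: 0.1625 / 18 = 0.0090 per month.
- Before month 1 (first telephone contact): 125 × (1 − e^−0.0198) = 2.45 and 125 × (1 − e^−0.0090) = 1.12, together about 3.6.
- Before month 2 (first on-site visit): 4.86 + 2.24 = about 7.1.
- By 18 months: 125 × 0.30 + 125 × 0.15 = 56.25.

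**Deaths before the first dose.** Over both arms the rate is 125 × (0.0198 + 0.0090) = 3.6 per month, or about 0.12 per day. If every patient took a week to start, about 0.8 deaths would be expected in that week. Drug is handed out at the randomisation visit (Section 5.1, Baseline Visit 1), so the likely number is lower.

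**Weight of one death.** The log-rank variance is about D/4. Dropping one death from one arm moves observed minus expected by about 0.5. With D = 56, the change in z is 0.5 / √14 = 0.13. A result at z = 1.96 (one-sided p = 0.025) becomes about 0.018 or 0.034, depending on the arm.

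**Completed-contact reading, by simulation** (125 per arm, every patient followed 18 months, 20,000 runs)

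| Deaths dropped | Type I error | Power |
|---|---|---|
| None | 0.026 | 0.825 |
| Before month 1, both arms | 0.024 | 0.798 |
| Before month 2, both arms | 0.024 | 0.766 |

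The simulation error at 0.025 is √(0.025 × 0.975 / 20,000) = 0.001, so type I error is preserved. Power is lost because real deaths are thrown away. The base of 0.825 is lower than the analytic 0.862 for 250 patients because it allows 18 months per patient rather than 18 to 24.

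Two further cases rest on assumptions that the protocol does not give. If early deaths were lost from the experimental arm alone, one-sided type I error would be about 0.047. If the drug caused 3 or 5 extra deaths in the first month and was otherwise without effect, dropping month-1 deaths in both arms would raise the chance of declaring benefit from 0.009 to 0.025, or from 0.005 to 0.027.

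**The case against.** A reader might infer that the rule selects patients by outcome. The documents do not establish that. The dose condition depends on exposure. The assessment condition depends on whether outcome data exist, not on what they show. Section 6.1 makes date of death the efficacy variable and Section 7.3.1 says it will be known for all who die, so the more natural reading keeps a death after the first dose. A patient who leaves alive early has a survival time from the termination date, and Sections 3.7.3 and 5.3 ask for an early termination visit.

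A reader might also infer that a few exclusions would decide the trial. One death moves p noticeably only when the result is at the boundary and the loss falls on one arm. With matching tablets and a blinded patient and investigator, nothing in the protocol suggests that patients in one arm would fail to start treatment more often. That objection stands, and it limits the size of the point.

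It can further be said that Section 7.2 prints its conditions openly and leaves a more detailed description of the sets to the SAP. This holds in part: the SAP could say that a death counts as an assessment. It does not cover the dose condition, which the protocol itself fixes. Nor is an all-randomised analysis listed anywhere.

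**Conclusion.** The defect is in the definition and the label. The confirmatory set is a modified ITT set, it rests on two conditions that the endpoint does not need, and one of them is undefined for time to death. If a recorded death counts as an assessment, the loss is confined to undosed patients and probably amounts to less than one expected death. If a completed contact is required, about 3.6 deaths before month 1 would be lost, with a power cost of just under three percentage points and no type I inflation when both arms are treated alike.

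These figures assume constant hazards at the protocol's 70% and 85% and 250 patients randomised. The cases with inflated error are illustrations and not expectations. The small expected effect makes this something that should be fixed, not a threat to the trial's validity. Left as it is, the report would describe as ITT a comparison that is not one.

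**What to change.** In Section 7.2, define the confirmatory ITT set as all randomised patients, analysed in the arm assigned, whether or not they were dosed or later assessed. State that every known death counts, and that patients without later contact are censored at the last date known alive, or at randomisation if there is none. Keep the present definition under a different name, such as modified ITT, as a sensitivity set.

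The cost is wording in the protocol and the SAP. Section 7 asks for a protocol amendment for major changes to the primary analysis, so this belongs in one, dated before unblinding. The planned 250 patients, the visits and the test stay as they are. Undosed patients in the experimental arm may dilute the effect slightly, which is part of what an ITT analysis estimates.

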## 7.3 Efficacy analyzes

The primary objective of this trial is to show the superiority of the test treatment compared to the standard treatment in terms of survival time.

## 7.3.1 Definition and analysis of primary endpoint

The primary endpoint is survival time, i.e. the time until death or the time until last contact to patient. Mortality is exclusively defined as death. Survival time will be calculated as difference from date of last contact and date of randomization. Date of last contact is defined as

- date of death for patients who will die during trial
- date of study termination for patients who are alive if date of study termination > date of last visit, otherwise the date of last visit will be used as date of last contact

### Replacement of missing values for ITT analysis:

Date of death will be known for all patients who will die during trial. For patients who are alive at end of study/last contact, the following replacement of missing date will be performed. Any date of last contact with unknown day (xx/NA/xxxx) in patients who are alive will be replaced with the date for mid-month (xx/15/xxxx). Dates of last contact with unknown day and month or with unknown day and month and year will not be replaced.

### Analysis of primary endpoint:

The statistical hypotheses are the following:

 $H_0: \qquad \lambda_2/\lambda_1 {\geq} 1$ 

 $H_1$ :  $\lambda_2/\lambda_1 < 1$ 

where  $\lambda_2/\lambda_1$  is the hazard ratio,  $\lambda_1$  denotes the hazard in the control group,  $\lambda_2$  denotes the hazard in the experimental group. The hazard ratio is assumed to be constant across time. The null hypotheses will be tested using the logrank test. The type one error is set to alpha=0.025 (one-sided). For estimating the treatment effect, the hazard ratio, incl. the one-sided 97.5% confidence interval will be provided.

Only the ITT analysis of the primary endpoint will be regarded as confirmatory. All other analyzes of primary endpoint will be regarded as exploratory.

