Statistical analysis	
 
Efficacy: The ITT analysis of the primary endpoint will be done in a confirmatory manner. All other analyzes of primary endpoint, all analyzes of the secondary endpoints, and all safety analyzes are exploratory. For confirmatory data analysis, the log-rank test (one-sided) will be performed. Additionally, the difference in the survival rate (18 months survival) between control group and experimental group will be calculated, incl. 97.5% confidence interval.
 
For further analyzes of primary endpoint, Kaplan-Meier-plots and log-rank-tests will be used.
 
Secondary endpoints: The secondary endpoints will be analyzed descriptively. Differences between experimental group and control group will be investigated using the Mann-Whitney-U-test.
 
Safety: Listing of adverse events, performing of chi-square tests to compare frequencies between control group and experimental group.
 

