## 3.6 Measures taken to minimize/avoid bias

#### 3.6.1 Randomization

This trial has two parallel groups (rasagiline versus placebo as add-on to standard treatment with riluzole), is randomized, and treatment groups are completely masked (double-blind trial). The randomization will be performed stratified according to bulbar onset or spinal onset of the disease, and separate for each trial center.

At the screening visit (V0), each patient will receive the next consecutive screening number.

At the randomization visit (V1), each patient eligible for study participation will receive the next consecutive randomization/patient number according to his stratum (bulbar onset vs. spinal onset) from a block of randomization numbers per site. Patients will be assigned to the bulbar or spinal stratum according to the location of the earliest experienced ALS symptom (defined by the first muscle weakness, or in the case of bulbar onset, by the presence of dysarthria and/or dysphagia). In the case of a patient with simultaneous onset of spinal and bulbar symptoms, onset will be defined as bulbar. Cervical and respiratory onsets are stratified to the spinal-onset stratum. This stratum assignment must be consistent with the diagnosis and clinical assessment (i.e., maximum score on bulbar scale and low score on manual muscle testing would contradict the assignment to bulbar stratum). The randomization list will be generated by the Institute of Epidemiology and

Medical Biometry Ulm University, Germany, using a validated system, which involves a pseudorandom number generator to ensure that the resulting treatment sequence will be both reproducible and non-predictable. Study medication will be packed by TEVA Pharma GmbH and blinded by the Pharmacy of the University Hospital Ulm, Germany, according to the randomization list. Each patient medication bottle will be sent together with the sealed unblinding codes to the sites. The investigator at the site takes care that each patient will be provided with the study medication box of the correct randomization number.

The randomization list will be kept in safe and confidential custody at Pharmacy of the University Hospital Ulm, Germany.

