## 7.1 Sample size

The sample size calculation is based on a comparison of two survival curves using the one-sided log-rank test. Following assumptions were made: Type one error 0.025, power 0.80, recruiting time 6 months, length of follow up period 18 months, 18 month survival rate of 70 % in the control group, 18 month survival rate of 85 % in the experimental group. Under the assumption of equal number of patients in each group, this scenario requires 106 patients in each group, i.e.  $2 \times 106 = 212$  patients in whole trial.

A previous study [GERP ALS-Study; pioglitazone in ALS; NCT00690118, clinicaltrials.gov ID] showed a drop-out rate of about 15 %, screening failure was observed in about 10 %. Thus, in total 250 patients have to be allocated (with consideration of a drop-out rate) and a total number of 278 patients have to be assessed for eligibility.

The sample size calculation was performed using SAS® software, version 9.2, procedure power.

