## 7.3.3 Analysis of Subgroups

Subgroup analyzes will be performed for the bulbar and spinal stratum.

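### Randomisation is stratified by bulbar versus spinal onset, but the confirmatory log-rank test and hazard ratio do not use the stratum; the cost is small and avoidable if onset is prognostic

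*Protocol*

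**What the plan says.** Section 3.6.1 of the protocol sets the allocation: "The randomization will be performed stratified according to bulbar onset or spinal onset of the disease, and separate for each trial center". It also gives rules for assigning patients to a stratum: simultaneous onset counts as bulbar, and cervical or respiratory onset as spinal. The stratum is therefore recorded for every patient at randomisation.

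The confirmatory analysis is described in three places, and none of them names a stratum:

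- Synopsis, statistical analysis: "For confirmatory data analysis, the log-rank test (one-sided) will be performed".
- Section 7.3.1: "The null hypotheses will be tested using the logrank test", and for the estimate, "For estimating the treatment effect, the hazard ratio, incl. the one-sided 97.5% confidence interval will be provided".
- Section 7.1 sizes the trial on a "comparison of two survival curves using the one-sided log-rank test".

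Onset is used in the analysis only in section 7.3.3: "Subgroup analyzes will be performed for the bulbar and spinal stratum". The protocol gives no expected bulbar share and no survival rate by stratum.

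**The concern.** When allocation is balanced within strata, the analysis normally respects those strata. The variance of an unstratified log-rank test does not allow for that balance. If onset predicts death, the observed-minus-expected difference varies less than this variance implies, so the test is conservative. It also compares risk sets that mix patients with different prognosis, and the hazard ratio is then a marginal one, slightly closer to 1 than the ratio within strata.

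What is at stake is a little power in a trial that expects only about 50 deaths, and agreement between design and analysis. The stratum is already recorded, so using it needs no new data.

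**Working it through.** **Inputs from section 7.1.** "Type one error 0.025, power 0.80, recruiting time 6 months, length of follow up period 18 months". Assumed survival at 18 months is 70% for control and 85% for experimental patients. The result is 106 per group (212 in total); with 15% drop-out, 250 allocated.

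**The plan's own figure.** Implied hazard ratio = ln 0.85 / ln 0.70 = (−0.1625)/(−0.3567) = 0.456. The check used a Lakatos-type calculation for an unstratified log-rank test, with exponential survival, uniform accrual over 6 months and at least 18 months of follow-up. It gives 106 per group at power 0.802. For drop-out, 212/0.85 = 249.4, so 250. The stated sample size therefore reproduces, and it belongs to the unstratified test.

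**Tests compared.** Unstratified: Z = (O − E)/√V, with E the sum of p and V the sum of p(1 − p) over deaths, where p is the share of the risk set in the experimental group. Stratified: Z = Σ(O_k − E_k)/√ΣV_k over the two onset strata, with risk sets formed within each stratum.

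**Assumptions not in the protocol.** Bulbar share 25 to 40%; bulbar:spinal hazard ratio 1, 1.5, 2 or 3; the same treatment hazard ratio in both strata.

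**Setting A.** 106 per group, accrual and follow-up as in section 7.1, no drop-out, overall 18-month survival held at 70% and 85%, 8,000 simulated trials per cell. Power in %, unstratified → stratified:

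| Bulbar:spinal ratio | share 25% | share 30% | share 40% |
|---|---|---|---|
| 1.0 | 80.7 → 80.6 | 80.9 → 80.9 | 80.9 → 80.9 |
| 1.5 | 81.1 → 81.2 | 80.5 → 80.4 | 82.3 → 82.3 |
| 2.0 | 81.5 → 81.9 | 81.5 → 82.0 | 81.8 → 82.5 |
| 3.0 | 82.2 → 83.4 | 81.1 → 83.0 | 81.5 → 83.3 |

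The standard error of one power figure is √(0.8 × 0.2/8000) = 0.45 points. Both tests were applied to the same simulated trials, so the differences within a cell are more precise than that.

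**Setting B.** 125 per group, 15% drop-out, 18 months per patient, hazard ratio 0.456 held within each stratum, 12,000 trials per cell:

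| Bulbar:spinal ratio | share 25% | share 33% |
|---|---|---|
| 1.5 | 78.7 → 79.0 | 79.0 → 79.4 |
| 2.0 | 78.2 → 79.0 | 77.8 → 78.8 |
| 3.0 | 76.8 → 79.4 | 76.6 → 79.3 |

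Further runs with 125 per group, 15% drop-out, 18 months per patient and a 30% share gave gains of 0.6 to 1.2 points at ratio 2 and 2.2 to 2.7 points at ratio 3. With onset not prognostic there was no visible cost.

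**Type I error (one-sided).** In setting A at 30% share (20,000 trials), the unstratified test gave 2.5, 2.2 and 2.1% at ratios 1.5, 2 and 3; the stratified test gave 2.5, 2.3 and 2.6%. With 125 per group, drop-out and 18 months per patient, the unstratified test gave about 2.0 to 2.3% at ratios 2 and 3.

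**Attenuation, share 30%, ratio 3.** Let x be 18-month spinal survival in the control group: 0.7x + 0.3x³ = 0.70 gives x = 0.789. In the experimental group 0.7y + 0.3y³ = 0.85 gives y = 0.901. The within-stratum hazard ratio is ln y/ln x = 0.1044/0.2366 = 0.441. At ratio 2 it is 0.450, against 0.456 marginal.

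**Centre.** The mean 18-month death probability is (0.30 + 0.15)/2 = 0.225, so 212 patients give about 48 deaths. With section 7.1's accrual and follow-up it is 0.256, or about 54 deaths. Over 15 × 2 = 30 centre-by-onset cells that is fewer than 2 deaths per cell.

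**The case against.** The strongest reply is that nothing is lost against the plan. The 106 per group was computed for a plain log-rank test, and that test delivers the stated power under section 7.1's own assumptions. This stands. A reader might infer that leaving out the stratum takes the trial below 80%, but the documents do not support that. The lower level in setting B comes from following each patient for 18 months only, which is a separate matter. The fall of its unstratified figures as the ratio rises comes from holding 0.456 within strata: at ratio 3 that lowers overall experimental survival to 84.6%, whereas section 7.1 assumes 85%. With 85% held, unstratified power stays at 78 to 80% throughout, and at ratio 3 it is about 80%, against about 82% stratified. Only the difference between the two tests is attributable to stratification.

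A reader might also infer that the test is invalid, or that onset was chosen because it affects survival. Neither is supported. The unstratified type I error is at or below 2.5%, a marginal hazard ratio is a legitimate quantity, and the protocol gives no reason for the stratification.

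Finally, the protocol is silent on strata and does not exclude them, and section 7 leaves details to a statistical analysis plan that was not available here. That limits the point but does not remove it. The test is named three times without a stratum, and section 7 requires major changes to the primary analysis to be reflected in a protocol amendment, so the protocol is the place to settle it.

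**Conclusion.** The mismatch between randomisation and confirmatory analysis is in the text; its consequence is small. The planned test is valid. If onset is prognostic, it is slightly conservative (about 2.0 to 2.3% at bulbar:spinal ratios 2 and 3) and gives up about 0.4 to 1.2 points of power at ratio 2 and about 1.2 to 2.7 points at ratio 3. At ratios 1 to 1.5 the difference is about zero. The within-stratum hazard ratio matching the planned survival rates is about 0.44 to 0.45, against 0.456 marginal.

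These sizes rest on an assumed bulbar share of 25 to 40% and on assumed prognostic strength, neither of which the protocol states. Severity: minor.

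**What to change.** Before unblinding, state in section 7.3.1 and in the synopsis that the confirmatory one-sided log-rank test is stratified by onset (bulbar/spinal), and that the hazard ratio comes from a Cox model stratified by onset. Leave centre out of the strata and give the sparse cells as the reason. Report the unstratified log-rank test as a sensitivity analysis.

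The cost is a protocol amendment in wording only, with matching text in the statistical analysis plan and no new data. The one change in interpretation is that the reported hazard ratio is then within-stratum rather than marginal, which should be said when it is compared with the 0.456 implied by the sample size.

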#### 3.7.1 Inclusion criteria

Patients meeting all of the following criteria will be considered for admission to the trial:

- Possible, probable (clinically or laboratory) or definite ALS according to the revised version of the El Escorial World Federation of Neurology criteria
- Disease duration more than 6 months and less than 3 years (inclusive). Disease onset defined as date of first muscle weakness, excluding fasciculations and cramps
- Vital capacity more than 50% of normal (slow vital capacity; best of three measurements)
- Age: ≥ 18 years
- Continuously treated with 100 mg riluzole for at least four weeks
- Capable of thoroughly understanding all information given and giving full informed consent according to GCP
- Women of childbearing age must be non-lactating and surgically sterile or using a highly
  effective method of birth control and have a negative pregnancy test. Acceptable methods of
  birth control with a low failure rate i.e. less than 1% per year) when used consistently and
  correct are such as implants, injectables, combined oral contraceptives, hormonal intrauterine
  devices (IUDs), or double-barrier methods (condom or diaphragm with spermicidal agent or
  IUD), sexual abstinence or vasectomized partner

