### Baseline Visit 1 (V1)

Patients eligible for study participation will enter the study site within 4 weeks after the screening visit and will be randomized to one of the treatment arms.

Blood samples for the determination of blood cell count, creatinine, CK, ASAT, ALAT and blood glucose, will be obtained. A blood sample for genetic testing will be collected as outlined in section 6.3.3. if the patient provided consent to this analysis. Body weight, blood pressure and radial pulse will be documented and lung function will be assessed by measuring the patient's vital capacity. In addition ALSFRS-R and SEIQoL will be performed. The patient will receive study medication according to the randomization list and a study participant card (see appendix VIII).

Any changes in the concomitant medication and adverse events before and during visit 1 will be documented.

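### The confirmatory survival analysis names no baseline covariate; pre-specified adjustment would be a cheap gain in efficiency, not the repair of an error

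*Protocol*

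**What the plan says.** **Test and estimate.** Protocol section 7.3.1 says: "The null hypotheses will be tested using the logrank test". The level is one-sided 0.025, and only the ITT analysis is confirmatory. On the size of the effect it says: "For estimating the treatment effect, the hazard ratio, incl. the one-sided 97.5% confidence interval will be provided". The model that yields the hazard ratio is not stated. The Synopsis repeats the one-sided log-rank test and, for further analyses of the primary endpoint, lists only Kaplan-Meier plots and log-rank tests. Neither place names a covariate or a stratification.

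**Sample size.** Section 7.1 rests on the same test: "Type one error 0.025, power 0.80, recruiting time 6 months, length of follow up period 18 months", with "18 month survival rate of 70 % in the control group" and "18 month survival rate of 85 % in the experimental group". This gives 106 per group, and 250 in total after 15% dropout.

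**Baseline data.** Age is recorded at screening. The date of onset is needed to check the disease-duration criterion (section 3.7.1). Vital capacity is measured at V0 and V1 (section 5.1). For V1 the protocol adds: "In addition ALSFRS-R and SEIQoL will be performed".

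**Randomisation and amendments.** Randomisation is stratified by bulbar or spinal onset and done separately by centre (section 3.6.1). Section 7 leaves detail to the SAP but requires a major modification of the primary analysis to appear in a protocol amendment as well.

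**The concern.** Entry is wide. Section 3.7.1 admits possible to definite ALS, age 18 with no upper limit, more than 6 months and up to 3 years since onset, and any sVC above 50% of normal. Patients will therefore start with different expected survival. Age, duration, sVC and ALSFRS-R are not randomisation factors, so they are balanced only by chance.

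In a time-to-event analysis, a test that uses strong baseline predictors can detect a given difference in group survival with higher probability than one that ignores them. With around 50 deaths and power set at the usual 80%, a few points are worth having, and the data are already collected. An adjusted estimate also makes the result easier to interpret if the groups happen to differ in stage of disease.

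**Working it through.** **1. The plan's own figure.** Planning hazard ratio = ln(0.85)/ln(0.70) = (-0.1625)/(-0.3567) = 0.456. The Lakatos log-rank calculation (uniform accrual 6 months, 18 further months, one-sided 0.025) gives 212 patients (106 per group), power 80.2%, 54.4 deaths. Dropout: 212/0.85 = 249.4, so 250. Screening: 250/0.90 = 277.8, so 278. All three figures reproduce.

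**2. Expected deaths.** The mean 18-month death risk is (0.30 + 0.15)/2 = 0.225.
- 212 patients, 18 months each: 212 × 0.225 = 47.7
- 250 patients, 18 months each, 15% loss: 52.1
- 212 patients, 6 + 18 month design: 54.4
- 250 patients, 18 months each, no loss: 250 × 0.225 = 56.25

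The range is 48 to 56.

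**3. Power of the planned test.** Section 3.1 plans 18 months per patient. With 250 patients and 15% loss, Lakatos gives z = 2.742 - 1.960 = 0.782, or 78%. Simulation gives 79 to 80%.

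**4. Effect of adjustment.** The protocol gives no prognostic strength, so it is an assumption: the SD of the combined baseline log-hazard, spread equally over four independent normal covariates. The hazard ratio between an upper- and a lower-quartile patient is exp(2 × 0.6745 × SD), which is about 2.0, 2.8 and 3.9 at SD 0.5, 0.75 and 1.0. Setting: 250 patients, 15% loss, 18 months each, group survival held at 70% and 85%, one-sided 0.025, 10,000 trials per row.

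| Assumed SD | Log-rank power | Adjusted Cox (Wald) power | Change, points |
|---|---|---|---|
| 0 | 79.1% | 78.0% | -1.1 |
| 0.3 | 79.4% | 79.1% | -0.3 |
| 0.5 | 79.3% | 80.7% | +1.4 |
| 0.7 | 79.1% | 82.4% | +3.3 |
| 1.0 | 80.0% | 88.1% | +8.1 |
| 1.3 | 80.1% | 92.6% | +12.5 |

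The Monte Carlo standard error of each power is √(0.8 × 0.2/10,000) = 0.4 points.

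Two further simulations of 3,000 trials per setting (standard error 0.7 points) agree:
- One gave 79.3 to 78.7%, 79.3 to 81.0%, 79.1 to 83.9% and 79.5 to 87.2% at SD 0, 0.5, 0.75 and 1.0.
- The other gave 79 to 79%, 81 to 85% and 80 to 88% at SD 0.5, 0.75 and 1.0.

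In patients, the gain is the squared ratio of (1.960 + z of power), adjusted over log-rank:
- SD 0.7: (1.960 + 0.929)²/(1.960 + 0.809)² = 1.09, or about 9% more patients.
- SD 1.0: (1.960 + 1.180)²/(1.960 + 0.840)² = 1.26, or about 26% more.

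**5. Covariate-adjusted log-rank test.** With linear augmentation and 3,000 trials per setting, power goes from 79.2 to 81.3%, 78.8 to 82.8% and 78.9 to 85.0% at SD 0.5, 0.75 and 1.0. The gains are +2.1, +4.0 and +6.1 points.

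**6. Type I error.** Under the null, with 10,000 trials per setting, both the log-rank and the adjusted Cox test reject in about 2.4 to 2.8% of trials (nominal 2.5%).

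**7. What the adjusted ratio estimates.** With group survival held at 70% and 85%, the conditional hazard ratio is 0.444, 0.431 and 0.405 at SD 0.5, 0.7 and 1.0, against 0.456 for the planning ratio.

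**The case against.** The unadjusted log-rank test is valid, tests the hypothesis written in section 7.3.1, and is the test on which the sample size was built; 106 per group reproduces exactly. The hazard-ratio model and supportive covariate analyses are commonly left to the SAP, which is not at hand. The gain rests on a prognostic strength found nowhere in the protocol and is negligible at SD 0.5 or below. The simulations are also favourable: independent normal covariates, the correct linear form, no missing values. All of this stands, and it limits the point to one of efficiency. It does not remove it. The Synopsis confines further primary analyses to Kaplan-Meier plots and log-rank tests, and section 7 makes a change of confirmatory test a protocol matter.

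A reader might infer four stronger claims that the protocol does not support.
- **Heterogeneity eats into the planned power.** It does not: section 7.1 states survival rates for whole groups, and with those held fixed log-rank power stays at 79 to 80% at every SD. It would fall (to 69.6% at SD 1.0, 4,000 trials) only if the planning ratio were meant as a ratio within covariate levels, which section 7.1 does not say.
- **Chance imbalance biases the result.** It does not: it is already reflected in the test's type I error, which stays near nominal.
- **The hazard ratio is fixed as unadjusted.** This is the natural reading beside a log-rank test, but the model is not stated.
- **The gain costs nothing.** It has the costs listed under the fix.

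**Conclusion.** The point holds as an efficiency recommendation. The protocol fixes a log-rank test and names no baseline covariate for the test or the hazard ratio, although four candidate prognostic measures are in hand before treatment and only about 48 to 56 deaths are expected. The planned analysis is neither wrong nor biased and has about the power claimed for it. With an assumed SD of the baseline log-hazard of 0 / 0.5 / 0.75 / 1.0, adjustment changes power by about -1 / +1.5 / +4 to +5 / +8 points with a Cox Wald test. With a covariate-adjusted log-rank test the gain at SD 1.0 is about 6 points. The result rests on that assumed range, on 250 patients with 15% loss and 18 months each, and on correctly specified covariates. The gain is material only if the covariates are strongly prognostic, but the possible loss is small.

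**What to change.** **Estimate.** In section 7.3.1, before unblinding, pre-specify a short covariate list: age, disease duration, sVC as % of normal, and ALSFRS-R total. Add the randomisation stratum of bulbar or spinal onset. Report a Cox hazard ratio adjusted for these beside the unadjusted one. This leaves the confirmatory test untouched and costs only wording.

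**Test, if the sponsor wants the power gain.** Make the confirmatory test the covariate-adjusted, onset-stratified log-rank test at one-sided 0.025, with the plain log-rank test as sensitivity analysis. Under section 7 this needs a protocol amendment, so it is more than a change of wording.

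**Costs.** The adjusted Cox hazard ratio is conditional on the covariates and is not the planning ratio of 0.456, so the report must say which is which. The form of each covariate and a rule for missing baseline values must be fixed in advance. About 1 point of power is lost if the covariates carry no information. No extra patient or measurement is needed.
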